Ganoderma lucidum is a species from *Ganodermataceae* family that has Beta-1,3/1,6-D-Glucan as one of active compound from isolated mycelium extract *Ganoderma lucidum*. This compound has biologic effect as immunomodulator and has been used to prevent and treat diseases such as gastric ulcer, arthritis, atherosclerosis, asthma, diabetes, cancer and other diseases related to immune disorders.^{10,11} A study on patient with CD showed that *Ganoderma lucidum* decrease TNF- α , IFN- γ , IL-17A from inflammation of intestinal mucosa.⁹ On the other hand, there is no study about the role of Beta-1,3/1,6-D-Glucan *Ganoderma lucidum* in UC.

Objective

General objective

To know the role of Beta-1,3/1,6-D-Glucan from mycelium extract of *Ganoderma lucidum* administration in ulcerative colitis

Specific objectives

1. To know the quality of life from patient with ulcerative colitis after Beta-1,3/1,6-D-Glucan mycelium extract of *Ganoderma lucidum* administration
2. To know the level of inflammatory marker from patient with ulcerative colitis after Beta-1,3/1,6-D-Glucan mycelium extract of *Ganoderma lucidum* administration
3. To know the Mayo score from patient with ulcerative colitis after Beta-1,3/1,6-D-Glucan mycelium extract of *Ganoderma lucidum* administration

Methods

Study Design

This research is a double blind, randomized clinical trial method. Analysis will be conducted pre and post administration: control (placebo) and intervention (polysaccharide peptide *Ganoderma lucidum*) 3 times daily for 90 days.

Location and Time

This research will be conducted on Indonesia from August 2019 to December 2020

Population and Subject

Population

The population of this research is patients diagnosed with ulcerative colitis in Indonesia

Subjects Criteria

- Inclusion criteria

1. Subjects aged ≥ 18 years old
2. Ulcerative colitis patients who are treated by 5-ASA 3x500 mg
3. Agreed to participate

- Exclusion criteria

1. Allergic with *Ganoderma lucidum*

2. Ulcerative colitis patients who are treated by corticosteroid, immunosuppressive agent, biologic agent
3. Could not be randomised and participate in this study by clinical judgement

Drop Out Criteria

Drop out subjects are subjects who have signed the informed consent but decide to withdraw before research is completed

Estimated Sample Size

Minimum sample size is determined using the following equation for proportion equation.

$$N1 = N2 = \frac{(Z_{\alpha}\sqrt{2PQ} + Z_{\beta}\sqrt{P_1Q_1 + P_2Q_2})^2}{(P_1 - P_2)^2}$$

Description :

$$Z_{\alpha} = 1.96 \quad Z_{\beta} = 0.84$$

$$P_1 - P_2 = 0.2 \quad P_1 = 0.554^{12}$$

$N1 = N2 = 92.25$, thus with predicted drop out 10% the minimal sample for each group is 102 subjects

Randomization

Randomization is generated by computer and subjects will be given code and divided into two groups (control and intervention). Researcher and subjects are blinded to treatment.

Variables

Independent Variables

1. Intervention: administration of capsule contain Beta-1,3/1,6-D-Glucan as active form of polysaccharide peptide from mycelium extract *Ganoderma lucidum* 3 times daily
2. Control (placebo): administration of empty capsule 3 times daily

Dependent Variables

1. Quality of life; assessed by Indonesian validated SF-36 questionnaire
2. Erythrocyte Sedimentation Rate (ESR), C-Reactive Protein (CRP), Tumor Necrosis Factor Alpha (TNF- α) and Interleukin 6 (IL-6) from blood samples

3. Fecal calprotectin from stool examination
4. Mayo Score from colonoscopy
5. Biopsy

Procedure

1. Eligibility assessment

The subjects will be assessed for eligibility using inclusion and exclusion criteria.

2. Subjects sign the informed consent form
3. Randomization
4. Pre-administration

Before administration of polysaccharide peptide or placebo based on randomization, subjects will be analysed for his/her quality of life by SF 36 questionnaire, ESR, CRP, TNF- α , IL-6, fecal calprotectin, colonoscopy (Mayo Score) and biopsy.

5. Administration (90 days)

Subjects will be given *Ganoderma lucidum* and placebo that will be taken three times daily for 90 days. The drugs are given monthly to the subjects.

6. Compliance monitoring

Compliance monitoring of administration is conducted by the investigators coordinating with his/her family and checked monthly when the patients came to take the capsule for the next month

7. Post administration

[figure not shown]
After 90 days the subjects will be analysed for his/her quality of life by SF 36 questionnaire, ESR, CRP, TNF- α , IL-6, fecal calprotectin, colonoscopy (Mayo Score) and biopsy.

8. Data analysis

- a. Normality analysis using Kolmogorov-Smirnov (Normally distributed if $p > 0.05$)
- b. Bivariate analysis by comparing numeric data between two groups: if data is normality distributed using T-test, if not using Mann-Whitney test (significant if $p < 0.05$)
- c. Bivariate analysis by comparing categorical data between two groups: if data is normality distributed using T-test, if not using Mann-Whitney test (significant if $p < 0.05$)

- d. Bivariate analysis by comparing numeric data between preadministration and postadministration: if data is normality distributed using paired T-test, if not using Wilcoxon test (significant if $p < 0.05$)
- e. Bivariate analysis by comparing categorical data between preadministration and postadministration: if data is normality distributed using Mc Nemar test, if not using Wilcoxon test (significant if $p < 0.05$)

Study flow chart

Ethical committee approval

Approval from the Ethical Committee at the Faculty of Medicine Universitas Indonesia must be obtained before starting the trial.

References

7. Ng SC. Epidemiology of Inflammatory Bowel Disease: Focus on Asia. *Best Pract Res Clin Gastroenterol.* 2014.

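### The sample size is built on an unnamed yes/no event, no outcome is primary, and any of seven or eight outcomes can be called significant at p < 0.05

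*Combined protocol and SAP*

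**What the plan says.** - **Sizing.** Under Estimated Sample Size: "Minimum sample size is determined using the following equation for proportion equation". The inputs are Z_alpha = 1.96, Z_beta = 0.84, P1 = 0.554 (cited to reference 12) and P1 − P2 = 0.2. The result is 92.25 per group, "thus with predicted drop out 10% the minimal sample for each group is 102 subjects". The event, the arm to which 0.554 applies, and P2 itself are not stated. The title of reference 12 does not identify an event.
- **Outcomes.** Dependent Variables has five entries: "Quality of life; assessed by Indonesian validated SF-36 questionnaire"; four blood markers (ESR, CRP, TNF-alpha, IL-6); fecal calprotectin; "Mayo Score from colonoscopy"; and biopsy. No cut-off, responder rule or remission definition is attached to any of them. Neither this list nor the three specific objectives is ranked.
- **Tests.** Under Procedure, step 8 (Data analysis), item b is "Bivariate analysis by comparing numeric data between two groups", item c is "Bivariate analysis by comparing categorical data between two groups" and item d is "Bivariate analysis by comparing numeric data between preadministration and postadministration". Item e does for categorical data what item d does for numeric data. Each of the four uses p < 0.05. No hierarchy, adjustment or criterion for a positive trial is given.

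**The concern.** A power calculation is informative only for the outcome and test it was made for. Here it concerns a difference in the rate of some event, while the listed outcomes are scores, laboratory values and an undefined biopsy result. One cannot check whether 102 per arm is enough for the outcome that will carry the conclusion, because that outcome is not identified.

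The second problem follows from the first. With no primary outcome and a 0.05 threshold on every comparison, the plan does not say which result would make the trial positive. A report could lead with any outcome that reached significance and still be consistent with the plan.

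**Working it through.** **1. The plan's own sample size.** Inputs from Estimated Sample Size: Z_alpha = 1.96, Z_beta = 0.84, P1 = 0.554, difference 0.2. P is taken as the mean of P1 and P2. Since P2 is not given, both directions are tried.

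n = (1.96·√(2PQ) + 0.84·√(P1Q1 + P2Q2))² / 0.2²

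- P2 = 0.354 (P = 0.454): (1.96·√0.4958 + 0.84·√0.4758)² / 0.04 = (1.3801 + 0.5794)² / 0.04 = **95.99**
- P2 = 0.754 (P = 0.654): (1.96·√0.4526 + 0.84·√0.4326)² / 0.04 = (1.3186 + 0.5525)² / 0.04 = **87.52**

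Neither gives 92.25. An unpooled variance with P2 = 0.354 comes close, (1.96 + 0.84)² × 0.4758 / 0.04 = 93.25, but that is not the printed formula. The gap is small and the point does not rest on it.

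Dropout step: 92.25 × 1.1 = 101.5, which rounds up to 102; 92.25 / 0.9 = 102.5, which rounds up to 103. Conversely, 102 × 0.9 = 91.8, so about 92 evaluable per arm is used below.

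**2. Power at 92 per arm if a binary outcome was meant.** Power = Φ[(0.2·√92 − 1.96·√(2PQ)) / √(P1Q1 + P2Q2)].

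- P2 = 0.354: Φ[(1.9183 − 1.3801) / 0.6898] = Φ(0.780) = **78.2%**
- P2 = 0.754: Φ[(1.9183 − 1.3186) / 0.6577] = Φ(0.912) = **81.9%**

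Exact enumeration of the uncorrected chi-square test gives 77.3% and 82.4%.

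**3. What 92 per arm can detect on a numeric outcome.** Normal approximation: 2.80 × √(2/92) = 0.413 SD. With the t distribution, two-sided 0.05 and 80% power, it is **0.415 SD**. For Mann-Whitney under normality (efficiency 3/π): 0.415 / √(3/π) = **0.425 SD**. The plan gives no SD or target difference to set against these.

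**4. Chance of at least one false positive between arms.** Seven outcomes have a recognisable measure: SF-36 (counted once), ESR, CRP, TNF-alpha, IL-6, fecal calprotectin and Mayo score. Biopsy would be an eighth if tested. With no true effect and independent tests, 1 − 0.95⁷ = 0.302 and 1 − 0.95⁸ = 0.337. For correlated outcomes, equicorrelated normal test statistics were used; the correlations are assumptions.

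| Correlation between tests | 7 tests | 8 tests |
|---|---|---|
| 0 | 30% | 34% |
| 0.3 | 27% | 30% |
| 0.5 | 23% | 25% |
| 0.7 | 18% | 19% |

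The within-arm pre-post tests (items d and e) are not counted.

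**The case against.** The strongest reply is that the plan never claims to be confirmatory. Its objectives are worded as finding out, it says the compound has not been studied in ulcerative colitis, and a 0.05 label on single tests is not a rule for declaring the trial a success. The false-positive figures therefore answer a rule the plan does not state. They also depend on assumed correlations and on counting SF-36 as one test. This stands as a limit: the percentages are conditional. It does not remove the problem, because the plan does not call itself exploratory either, and a randomised, double-blind, placebo-controlled trial with a formal power calculation will be read as testing efficacy.

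A second reply is that item c covers categorical data, so a yes/no outcome could be tested there. Mann-Whitney on 0/1 data, corrected for ties, is essentially the uncorrected chi-square test. That is correct, so the lack of a named test of proportions is not the main defect. What is missing is the binary variable itself.

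Third, the event may be recoverable from reference 12, and the opening part of the document and the flow chart were not available for this review. The absence is therefore asserted only for the supplied text. Even if the reference identifies the event, the protocol still has to name it.

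**Conclusion.** The concern holds and must be fixed. In the supplied text, the 80% power is attached to no specified outcome, and no primary outcome or multiplicity rule is given. If any single outcome could support an efficacy claim, the between-arm false-positive rate is about 18% to 34%, depending on the number of tests and their correlation, against a nominal 5%. If a binary outcome was intended, actual power at 92 evaluable per arm is about 78% or 82%, depending on the direction of the difference. That discrepancy is minor; the undefined outcome is the substance. Confidence is high, subject to the parts of the document that could not be seen.

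**What to change.** Before unblinding, name one primary outcome and one primary between-arm test at two-sided 0.05, and make the power statement match. There are two routes.

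- **(a) Binary, if that was intended.** Define the event behind 0.554, state P2 and the direction of the difference, and name a chi-square test. Restate the power for 92 evaluable per arm: about 78% if P2 = 0.354, about 82% if P2 = 0.754.
- **(b) Numeric.** Make one numeric outcome primary, for example the Mayo score if it is analysed as numeric. Replace the proportion calculation with a statement that 92 evaluable per arm give 80% power for about 0.415 SD by t-test, or about 0.425 SD by Mann-Whitney. This describes what the existing size can detect; it does not justify the size.

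Under either route, label the other outcomes secondary (fixed order or Holm) or exploratory, say whether biopsy is tested and on what measure, and treat within-arm pre-post tests as descriptive. Date the amendment and record that the choice was made blind to results by arm. The study was scheduled for August 2019 to December 2020, so a choice made after unblinding could not be presented as prespecified.

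**Cost.** Wording only, if 102 per arm is kept. Nominal significance on a secondary outcome can no longer be offered as proof of efficacy. Under (a) with P2 = 0.354 the stated power falls to about 78%. Holding 80% would need 96 evaluable per arm, 96 / 0.9 = 106.7, so 107 randomised per arm, or 10 more patients in total.

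### The stated 92.25 per group does not follow from the plan's own formula and inputs, which give 95.99 or 87.52 depending on an unstated P2

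*Combined protocol and SAP*

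**What the plan says.** Under Estimated Sample Size the plan says: "Minimum sample size is determined using the following equation for proportion equation". The formula is the usual one for two independent proportions, with a pooled variance in the alpha term and separate variances in the beta term. The listed inputs are Z_alpha = 1.96, Z_beta = 0.84, P1 - P2 = 0.2 and P1 = 0.554, the last cited to reference 12. The result is given as N1 = N2 = 92.25, followed by "thus with predicted drop out 10% the minimal sample for each group is 102 subjects".

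The section does not give P2, define P, say which arm P1 describes, or name the outcome to which the proportions belong. The power is not written in words; 80% is implied by Z_beta = 0.84. The Dependent Variables section lists SF-36, blood markers, fecal calprotectin, Mayo score and biopsy, with no responder definition that would turn any of them into a proportion.

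**The concern.** A reader who puts the listed inputs into the printed formula does not get the printed answer. This calculation is the only quantitative justification for the size of a trial in which every patient has colonoscopy and biopsy before and after treatment, so it should be reproducible.

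The gap cannot be resolved from the text, because a difference of 0.2 from 0.554 allows two values of P2. The formula asks for more patients than stated under one and fewer under the other. At stake are the credibility of the derivation and the power that can be claimed for 102 per group.

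**Working it through.** **Inputs, all from Estimated Sample Size.** Z_alpha = 1.96, Z_beta = 0.84, P1 = 0.554 (Q1 = 0.446), difference 0.2, drop-out 10%. Assumption: P = (P1 + P2)/2 and Q = 1 - P, the standard meaning, since the plan does not define P.

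**Formula as printed.** N per group = (Z_alpha × √(2PQ) + Z_beta × √(P1Q1 + P2Q2))² / (P1 - P2)².

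**Attempt to reproduce 92.25.**

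*P2 = 0.354 (P1 - P2 = 0.2 taken literally).*
- P = 0.454; 2PQ = 2 × 0.454 × 0.546 = 0.4958, square root 0.7041.
- P1Q1 + P2Q2 = 0.2471 + 0.2287 = 0.4758, square root 0.6898.
- N = (1.96 × 0.7041 + 0.84 × 0.6898)² / 0.04 = 1.9595² / 0.04 = 95.99.

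*P2 = 0.754 (difference in the other direction).*
- P = 0.654; 2PQ = 2 × 0.654 × 0.346 = 0.4526, square root 0.6727.
- P1Q1 + P2Q2 = 0.2471 + 0.1855 = 0.4326, square root 0.6577.
- N = (1.96 × 0.6727 + 0.84 × 0.6577)² / 0.04 = 1.8710² / 0.04 = 87.52.

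The stated 92.25 is 3.9% below the first result and 5.4% above the second. To reach about 92.25 with P1 = 0.554, the difference would have to be about 0.204 downward or 0.195 upward.

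**Other routes to 92.25.**

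| Variant | P2 = 0.354 | P2 = 0.754 |
|---|---|---|
| As printed, P = mean | 95.99 | 87.52 |
| Unpooled variance throughout | 93.25 | 84.78 |
| Pooled variance throughout | 97.17 | 88.70 |
| P set to P1 | 95.77 | 93.15 |
| P set to P2 | 90.72 | 76.23 |

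None gives 92.25. The unpooled result at P2 = 0.354 is 1.00 above it, which may point to a different formula plus a slip, but the documents cannot confirm that.

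**Drop-out step.** 92.25 × 1.10 = 101.5, rounded up to 102, which reproduces the plan's figure. A 10% loss from 102 leaves 102 × 0.90 = 91.8, which is 0.45 below 92.25. The correct inflation is 92.25 / 0.90 = 102.5, so 103.

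**Enrolment from the printed formula.**
- P2 = 0.354: 95.99 / 0.90 = 106.7, so 107 per group (214 in total, against 204 planned).
- P2 = 0.754: 87.52 / 0.90 = 97.2, so 98 per group (196 in total).

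**Power of 102 per group.** Solving the formula for the beta term: Z_beta = (0.2 × √n - 1.96 × √(2PQ)) / √(P1Q1 + P2Q2).

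| Evaluable per group | P2 = 0.354 | P2 = 0.754 |
|---|---|---|
| 91.8 (10% lost) | 78.2% | 81.8% |
| 102 (none lost) | 82.3% | 85.7% |

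For example, with n = 91.8 and P2 = 0.354: (0.2 × 9.581 - 1.3801) / 0.6898 = 0.777, which corresponds to 78.2%.

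**The case against.** A reader might infer that 102 per group leaves the trial short of 80% power. The documents do not support that. After 10% loss the shortfall appears only if P2 = 0.354, and there it is 1.8 points; if P2 = 0.754, power is 81.8% and the formula needs only 98 per group. The context may even lean towards the second reading. The cited source of P1 is titled as a review of conventional therapy, and the trial adds capsule or placebo to background 5-ASA, so P1 could be a control rate that treatment is meant to raise. That too is inference, because the endpoint is unnamed and the source cannot be checked here. This part of the objection stands.

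It is also fair to say that the drop-out slip is trivial: one enrolled patient per group, and on the P2 = 0.754 reading 91.8 evaluable still exceeds the 87.52 required. This stands as well.

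A third objection is that the formula, not the number, may be the slip, since an unpooled version comes within 1.00 of the stated figure. That limits what can be asked: the two must be reconciled, with no presumption about which is wrong. It does not rescue the text, because the printed formula still did not produce the printed number.

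Finally, with no binary endpoint defined, neither 78% nor 82% is the power of any analysis the plan specifies. That is correct, and it is a reason to require the endpoint to be named. Nothing in the objections makes 92.25 reproducible.

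**Conclusion.** The figure of 92.25 is wrong as written. The printed formula and inputs give 95.99 or 87.52, and the plan omits what is needed to choose between them: P2, P, the arm P1 describes and the endpoint. This rests on taking P as the mean of the two proportions; the alternatives tried do not give 92.25 either.

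The practical size is modest. The formula's enrolment is 107 or 98 per group against the 102 planned, and power at about 92 evaluable is about 78% or about 82%. Whether the trial meets the implied 80% depends on which P2 was meant, so a failure to reach it is not established. The drop-out error is real but minor. The point concerns a sample-size justification that cannot be reproduced; it does not show a material loss of power.

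**What to change.** In Estimated Sample Size:

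1. State P2, define P, say which arm P1 = 0.554 describes, and name the binary endpoint and its responder definition.
2. Reconcile formula and figure. If the printed formula is kept, replace 92.25 with 95.99 (P2 = 0.354) or 87.52 (P2 = 0.754). If another formula was used, print that formula and its result.
3. Inflate for drop-out by dividing by 0.90.
4. Keep 102 per group as the enrolment figure and report the power it gives at about 92 evaluable: about 78% for P2 = 0.354, below the implied 80%, or about 82% for P2 = 0.754, above it. Show the formula's own enrolment (107 or 98) beside it, so that the choice of 102 is open to the reader.

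The cost is a rewrite of one paragraph, with no extra patients and no change to procedures. The downside is that on the literal reading the stated power becomes about 2 points less favourable.

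### The placebo is specified as an empty capsule against a filled active capsule, so the stated double blind is not secured

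*Combined protocol and SAP*

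**What the plan says.** The Study Design section states: "This research is a double blind, randomized clinical trial method". The Randomization section adds: "Researcher and subjects are blinded to treatment". Under Variables, Independent Variables, the two products are then defined. The intervention is "administration of capsule contain Beta-1,3/1,6-D-Glucan as active form of polysaccharide peptide", drawn from the mycelium extract. The comparator is "Control (placebo): administration of empty capsule 3 times daily".

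The safeguards described are a computer-generated list and a subject code: "Randomization is generated by computer and subjects will be given code and divided into two groups (control and intervention"). On supply, the Procedure section says: "The drugs are given monthly to the subjects". On adherence it says: "Compliance monitoring of administration is conducted by the investigators coordinating with his/her family", with a check each month when subjects come for their next supply. The dependent variables include "Quality of life; assessed by Indonesian validated SF-36 questionnaire", the Mayo score from colonoscopy, biopsy, ESR, CRP, TNF-alpha, IL-6 and fecal calprotectin.

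**The concern.** A placebo supports a blind only if it cannot be told from the active product in ordinary use. Read as written, one arm swallows a filled capsule and the other an empty shell. The shell is lighter and holds nothing, which is plain to anyone who opens one. A subject code conceals the label on the bottle, not the nature of the capsule inside it.

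Two of the three specific objectives, quality of life and Mayo score, rest on measures that belief about allocation can influence: the SF-36 through the subject's own answers, and the Mayo score through the assessor's judgement if the assessor learns or guesses the arm. Biopsy reading may be exposed in the same way, although the plan does not say how it is scored. A subject who discovers an empty capsule may also stop taking it or withdraw, and the plan states no method for handling withdrawals in the analysis. A bias of this kind does not shrink with sample size and cannot be reliably removed by analysis afterwards.

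**Working it through.** The plan gives no figure on this point to reproduce, so the check has two parts: a comparison of the text, and an illustration of size.

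**Comparison of the text**

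| Element | What the plan specifies | Where |
|---|---|---|
| Blinding claimed | Double blind; researcher and subjects | Study Design; Randomization |
| Active product | Capsule containing the extract | Independent Variables, 1 |
| Placebo product | Empty capsule | Independent Variables, 2 |
| Concealment measures | Computer-generated list, subject code | Randomization |
| Filler, or matching of weight, appearance or smell | Not described | – |
| Separate dispenser, separate blinded assessor, check of the blind | Not described | – |

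The first three rows do not fit together, and nothing in the remaining rows makes up the difference.

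**Opportunity to notice**

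- Three administrations a day × 90 days = 270 dosing occasions per subject.
- Supply is monthly, so the investigators who monitor compliance have contact with subjects around each hand-out.
- The family is involved in that monitoring and may also see or handle the capsules.

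**Illustration of size (by assumption)**

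Inputs:

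- n = 92 evaluable per arm, from the 92.25 per group under Estimated Sample Size, before the allowance for drop-out.
- Two-sided 5% test, critical value 1.96.
- No true treatment effect.
- b = the mean shift, in SD units, that unblinding produces between arms on a subjective outcome. The documents give no value, so b is set to 0, 0.1, 0.2 and 0.3.

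Standard error of a standardised mean difference:

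SE = √(2/92) = 0.1474 SD

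False-positive rate = P(|Z + b/SE| > 1.96), with Z standard normal.

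| b (SD) | b/SE | False-positive rate |
|---|---|---|
| 0 | 0 | 5% |
| 0.1 | 0.68 | about 10% |
| 0.2 | 1.36 | about 27% |
| 0.3 | 2.03 | about 53% |

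The sample size was derived for a comparison of proportions and is used here only to give a realistic n for a numeric outcome such as the SF-36.

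**The case against.** The best answer is that the word empty may be loose English for a capsule without active ingredient. The wording is imprecise elsewhere: the administration step, taken literally, gives both products to every subject. The intent to blind is stated twice. The trial is also parallel-group, so a subject has no routine side-by-side comparison, and the plan gives no fill weight, shell opacity, colour or smell from which to judge how easily the products could be told apart. Nothing shows that unblinding would in fact occur. The laboratory markers, which serve one of the three specific objectives, are much less open to expectation. The shifts of 0.1 to 0.3 SD are averages over a whole arm and have no support in the documents.

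Much of this stands as a limit on how strongly the point can be put. Unblinding is a risk, not an established event; the exposure is mainly in the SF-36 and Mayo score; the percentages are illustrative and start at 5% for no shift. It does not remove the point. The literal reading is the more natural one, and no part of the plan offers another. Under the looser reading the plan still misdescribes its comparator, and a reader cannot verify the blinding claim. Either way the text needs to change.

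**Conclusion.** The concern holds. As specified, the placebo differs from the active product in weight and contents, and no described measure offsets this, so the double blind is claimed but not secured. That conclusion rests on the text alone and does not depend on the calculation.

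The size is conditional. It assumes 92 evaluable subjects per arm, no true effect, and an unblinding shift of 0.1 to 0.3 SD on a subjective outcome; the false-positive rate is then about 10% to 53% instead of 5%. If few subjects or assessors detect the difference, the rate stays near 5%. Because the correction is easy and the bias cannot be reliably undone later, the sponsor should make the change, preferably before any capsules are dispensed.

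**What to change.** In Independent Variables, item 2, replace the empty capsule with wording such as: a capsule identical in shell, colour and size to the active capsule, filled with an inert excipient matched for weight and smell, and supplied in identical coded packaging. If the placebo is already made this way, only the description needs correcting.

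It would help to add to the Randomization section who holds the code and who dispenses the capsules.

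The cost is an inert filler, a minor manufacturing expense with some lead time, and a one-line amendment. The active product, the dosing schedule, the endpoints and the sample size are unchanged.

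### The available text provides for no recording or by-arm reporting of adverse events, so harms other than worsening still present at Day 90 would be lost

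*Combined protocol and SAP*

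**What the plan says.** **Contacts during treatment.** Procedure step 5 states that "The drugs are given monthly to the subjects". Step 6 has the investigators follow compliance with the help of the family, and compliance is "checked monthly when the patients came to take the capsule for the next month". The text gives these contacts no other content.

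**Assessments.** Step 4 (before treatment) and step 7 (after treatment) use one battery: SF-36, ESR, CRP, TNF-α, IL-6, fecal calprotectin, colonoscopy for the Mayo score, and biopsy. Step 7 begins "After 90 days the subjects will be analysed for his/her quality of life by SF 36 questionnaire, ESR, CRP" and adds no question about events since baseline. The Dependent Variables section lists the same items.

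**Objectives and analysis.** The three specific objectives concern quality of life, inflammatory markers and the Mayo score. Data analysis (step 8, items a to e) gives generic between-group and pre/post tests and names no safety outcome.

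**Nearest safety text.** One exclusion criterion concerns allergy to the product and applies before treatment. The Drop Out Criteria define drop-out as a participant's own decision to leave after consenting, and do not ask for a reason.

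**The product.** The text before the Objective says "This compound has biologic effect as immunomodulator" and that "there is no study about the role of Beta-1,3/1,6-D-Glucan *Ganoderma lucidum* in UC". The inclusion criteria admit "Ulcerative colitis patients who are treated by 5-ASA 3x500 mg", so it is given on top of existing treatment.

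**The concern.** The protocol calls the product an immunomodulator, says it is unstudied in ulcerative colitis, and gives it for 90 days to patients already on 5-ASA. A blinded, placebo-controlled comparison is a good setting in which to learn how well it is tolerated, and the patients are already seen each month. Yet none of the sections that define what is collected or analysed includes adverse events.

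This differs from an analysis left unspecified. A missing analysis can be written later from the data, but a transient event that nobody wrote down cannot be recovered. A withdrawal caused by an adverse event would also look like any other withdrawal, because the drop-out definition asks for no reason. The report could then describe benefit by arm but could say little about tolerability beyond what remains visible at the last visit.

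**Working it through.** **Step 1. What the described data would and would not show**

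| Kind of harm | Where it could appear in the plan | Captured? |
|---|---|---|
| Worse colitis still present at Day 90 | Mayo score, biopsy, calprotectin, blood markers; compared between groups under step 8b and 8c | Yes, in patients who return |
| Worse general health still present at Day 90 | SF-36; compared under step 8b | Yes, in patients who return |
| Colitis flare that resolves before Day 90 | Monthly contact: no item | No |
| Event unrelated to colitis | No dependent variable and no item in steps 5 to 7, apart from any effect on SF-36 or markers at Day 90 | Not as an event |
| Event behind a withdrawal | Drop Out Criteria: no reason requested | No |

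The gap is the last three rows.

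**Step 2. Numbers available**

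The plan states no figure on safety. The only relevant inputs are the sample sizes under Estimated Sample Size: 92.25 per group before drop-out and 102 after a 10% allowance. The step to 102 reproduces as 92.25 × 1.1 = 101.475, rounded up. If 10% of 102 leave, 102 × 0.9 = 91.8, or about 92 completers. How 92.25 was derived does not bear on this point.

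The documents give no adverse-event rates. All rates below are assumptions, shown over a range.

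**Step 3. Chance of seeing at least one case in the active arm**

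Formula: 1 − (1 − r)^n, for a true rate r and n patients. For example, 1 − 0.97^102 = 0.955.

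| Assumed rate | n = 102 | n = 92 |
|---|---|---|
| 1% | 64.1% | 60.3% |
| 2% | 87.3% | 84.4% |
| 3% | 95.5% | 93.9% |
| 5% | 99.5% | 99.1% |

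**Step 4. What zero cases would say**

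One-sided 95% upper limit: 1 − 0.05^(1/n).
- n = 102: 2.9% (rule of three: 3/102 = 2.9%).
- n = 92: 3.2% (rule of three: 3/92 = 3.3%).

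**Step 5. What a comparison of arms could show**

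Two-sided 0.05, normal approximation: power = Φ[(|p1 − p2|√n − 1.96√(2p̄q̄)) / √(p1q1 + p2q2)].

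For 5% against 10% with n = 102 per arm:
- p̄ = 0.075, so √(2 × 0.075 × 0.925) = 0.3725.
- √(0.05 × 0.95 + 0.10 × 0.90) = 0.3708.
- (0.05 × 10.0995 − 1.96 × 0.3725) / 0.3708 = −0.607, and Φ(−0.607) = 0.272.

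| Assumed rates | n = 102 per arm | n = 92 per arm |
|---|---|---|
| 5% vs 10% | 27% | 25% |
| 5% vs 15% | 67% | 62% |
| 5% vs 20% | 91% | 87% |

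Only large differences would be detected reliably. Recording would give estimates with intervals, not a confirmatory safety test.

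**The case against.** **Safety may be covered in parts not seen.** The opening part of the document, any consent pages and the flow chart were not available, and their absence here is not an omission by the sponsor. This stands as a limit. A reader might infer that no adverse event will be recorded anywhere in the trial; the documents do not support that. They support only that the available text specifies no such recording. However, the sections that define what is collected and analysed are present, and none refers to safety data held elsewhere. A reporting duty set out elsewhere would not by itself supply a comparison by arm.

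**Step 6 does not exclude other activity.** Correct. It describes a compliance check without saying that nothing else is done. Staff may well ask about symptoms or note why someone leaves, but without a form and a defined outcome this would depend on the site and the person.

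**The Day 90 measures show harm.** This stands in part. A reader might infer that the trial cannot see or compare harms at all. That is too strong: persisting worsening of colitis or general health is measured in both arms and compared.

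**Safety is not among the stated objectives.** True, so this is a design weakness and not an internal contradiction. The general objective, to learn the role of the product, does not by itself oblige the plan to measure harms.

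**The trial is too small to study harms.** Step 5 of the working confirms low power for modest differences. That supports a descriptive table; it is no reason to collect nothing.

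**Conclusion.** The point holds in a limited form. On the text available, adverse events are neither recorded nor reported by arm, and the monthly contacts are described only as dispensing and a compliance check. The loss covers non-colitis events, events that resolve before Day 90 and events behind withdrawals. It does not cover worsening that persists to Day 90 in patients who return.

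For scale, systematic recording in 102 active patients would very probably show at least one case of an event with a true rate of 3% or more (95.5% at 3%; 93.9% with 92 completers). It would miss an event with a rate of 1% about one time in three. Zero cases would put a one-sided 95% upper limit at 2.9% (3.2% with 92). These figures rest on assumed rates, independent patients and complete ascertainment. They show what recording could offer and do not estimate any actual risk of the product. The comparison between arms would be imprecise and should be presented as descriptive.

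The change is worth making before enrolment because it is cheap and the loss cannot be repaired afterwards.

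**What to change.** - **Collection.** At each existing monthly capsule visit and at Day 90, complete a short standard form under the blind. It should record adverse events, serious adverse events and patient-reported worsening of colitis since the last contact. Patient report is suggested because the plan has no disease measure at the monthly visits.
- **Withdrawals.** Record the reason and date for every participant who leaves, including whether an adverse event was involved.
- **Outcome and analysis.** Add a descriptive safety outcome to the Dependent Variables and to step 8: the number and percentage of patients with any adverse event, any serious adverse event, reported worsening, and withdrawal due to an adverse event, by arm, with the difference and its 95% CI. State that these comparisons are not powered.
- **If already covered.** If the parts not seen contain adverse-event procedures, cite them in steps 6 and 7 and add the by-arm table.

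**Cost.** A short form at visits that already take place, one table, and some staff time to follow up any serious event. No extra visit is needed and the sample size does not change. The change concerns data collection only and sets no rule for treatment.
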